Effects of Reading to Preterm Infants on Baby and Parents' Well Being

ID: 2014-1464

10/24/19

Study Protocol:

Parents of infants born between 23 and 31 weeks gestational age who were between 260/7 and 346/7 weeks post menstrual age cared for in the NICU were approached for enrollment into the study. All infants were at least 7 days or older after birth to allow successful transition to extra uterine life. Parents agreed to participate and to read out loud from written word as a requirement for participation in the study. Infants were excluded if: they were considered too ill to participate by the primary care team, were on high frequency ventilation, were not expected to survive, had chromosomal anomalies, had abnormalities of the midface, or had a family history of/suspected congenital hearing loss. The study was approved by the Georgetown University Institutional Review Board. Of 21 sets of parents approached, 18 consented to participate. Two sets of parents decided to participate only with live reading and did not make a voice recording. Parents were given a children's book using a rhyming pattern of text to read, but other materials were allowed according to parental preference. Parents were asked to read or create a recording lasting a minimum of 15 min but up to 60 min of recorded reading. Mothers and fathers could read to their infants individually. Recordings were made using Garage Band® on a study computer and exported to bedside ipods®. Recording was played via humidity resistant Bluetooth enabled speakers in the incubator. Recorded reading was played for infants up to twice per day by the bedside nurse. The primary care team could withhold any recorded or bedside reading exposure if an infant was deemed too unstable for that experience on any given day. Live and recorded reading could occur on the same day with the goal of at least 2 reading episodes per day, but because parents may not be available for live reading everyday, recorded and live reading episodes may occur on different days. Cardiorespiratory events for each reading exposure were compared to the immediate period before and after the reading exposure. As such the period before each reading exposure served as the control period for that reading exposure to mitigate the effect of reading on different days or time periods. All infants were being cared for in incubators on reading exposure days. For 2 infants, at one time period each, the infant was removed from the incubator and was being held for all comparison time points around that single reading exposure. Two infants had one day of data when the infant was held only during reading exposure. Data from those days were excluded from analysis. For all other live reading exposures, the infant was in the incubator with parents reading through the open portholes. Sound decibel levels were checked via a sound meter (Triplet SoniChek TSC-MC1 Mini Digital Sound Level meter) to ensure sound levels did not increase above baseline if above 45 decibels prior to reading exposure.

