
Cardiorespiratory data, including heart rate (HR), respiratory rate (RR), oxygen saturation, apnea and bradycardia events, were continuously downloaded every 5 seconds directly from bedside GE monitors using BedMaster EX Software and exported to a spreadsheet for analysis. The data on mode of respiratory support and amount of supplemental oxygen needed were collected for each time period. Mean RR, HR, apnea and bradycardia episodes, amount of supplemental oxygen needed, mode of respiratory support, if any, and number of periods with oxygen saturation <85% were compared to the reading period at 3 time points: 3 h before reading, 1 h before reading and 1 h after reading. These time points were chosen to provide a variety of time periods in relation to care times and feedings, including

day and nighttime periods. Results were compared using χ^2 test for categorical variables and student's t test for continuous variables. $P < 0.05$ was considered as significant.

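### The only inferential rule is P<0.05 with no confidence interval, so a non-significant instability result could not show how large a worsening has been ruled out

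*Combined protocol and SAP*

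**What the plan says.** The inferential plan is the last two sentences of the Study Protocol section. They read "Results were compared using χ^2 test for categorical variables and student's t test for continuous variables" and "P < 0.05$ was considered as significant". Neither sentence, nor anything else in the document, names a confidence interval, a target difference, a worsening to be excluded, or a power or sample-size basis. The document does not say whether the tests are paired or two-sided.

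The outcomes are respiratory rate, heart rate, apnea, bradycardia, supplemental oxygen, mode of respiratory support, and the count of low-saturation periods. They "were compared to the reading period at 3 time points: 3 h before reading, 1 h before reading and 1 h after reading".

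On numbers, the enrolment text gives "Of 21 sets of parents approached, 18 consented to participate" and adds "Two sets of parents decided to participate only with live reading and did not make a voice recording". The comparison is made per exposure: "Cardiorespiratory events for each reading exposure were compared to the immediate period before and after the reading exposure". Exposures repeat: "Recorded reading was played for infants up to twice per day by the bedside nurse". The numbers of infants, days, exposures and events are not stated.

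**The concern.** At least four of the seven outcomes (apnea, bradycardia, low saturation and oxygen need) get worse when an infant becomes less stable. The care team "could withhold any recorded or bedside reading exposure if an infant was deemed too unstable for that experience on any given day", so instability was plainly in mind when reading was delivered. Anyone using the results will ask whether reading made these events more frequent and, if no increase was detected, how large an increase can be set aside.

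A P value of 0.05 or more does not answer the second question. The same verdict of not significant can come from an interval that excludes all but a small rise, or from one that still includes a doubling. An interval computed from the same data separates the two cases. Without it, the reader cannot tell an informative null result from an uninformative one.

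**Working it through.** The plan states no sample size, power or event count, so it has no figure to reproduce. The calculations below show how far the answer moves across plausible inputs.

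**Inputs from the document:** a threshold of 0.05; 18 consenting families, of whom at most 18 − 2 = 16 could contribute recorded reading.

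**Assumed inputs:** two-sided tests, 18 infants, equal window lengths, event totals, variance inflation, exposures per infant, and within-infant correlation (ICC). Equal windows is a real assumption: readings last 15 to 60 minutes and the length of the comparison windows is not given.

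**1. Event outcomes.** Take E events in each of two periods, variance φ times the mean, and an observed rate ratio of exactly 1.0. The 95% limits are exp(±1.96·√(2φ/E)).

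| E per period | φ | 1.96·√(2φ/E) | 95% CI |
|---|---|---|---|
| 18 | 1 | 0.653 | 0.52–1.92 |
| 90 | 1 | 0.292 | 0.75–1.34 |
| 90 | 3 | 0.506 | 0.60–1.66 |

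Over a wider range, the upper limit is 2.40 (φ=1) or 5.77 (φ=4) at E=10, and 1.32 (φ=1) or 1.74 (φ=4) at E=100. With identical observed rates, the upper limit therefore runs from about 1.3 to above 5. All of these results would be reported simply as not significant.

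**2. Chance of missing a real rise.** For a true 50% increase over E baseline events, power is approximately Φ(ln 1.5 / √(φ(1/E + 1/(1.5E))) − 1.96).

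- E=18, φ=1: 0.405/0.304 − 1.96 = −0.63, power about 27%.
- E=90, φ=1: 0.405/0.136 − 1.96 = 1.02, power about 85%.
- E=90, φ=3: 0.405/0.236 − 1.96 = −0.24, power about 41%.

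In two of these three assumed settings a non-significant result is the likelier outcome despite the rise. In the third it is not.

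**3. Continuous outcomes.** With one paired difference per infant, the 95% half-width is t(0.975, n−1)/√n, in SDs of the difference. For n=18 this is 2.110/4.243 = 0.50 SD. For n=16 it is 0.53 SD.

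The plan compares each exposure, so repeated exposures add information. With m exposures per infant, the effective number is 18m/(1+(m−1)·ICC), and the half-width is approximately 2.11/√(effective number), in SDs of a single-exposure difference. For m=10:

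- ICC 0: effective number 180, half-width 0.16 SD.
- ICC 0.1: effective number 95, half-width 0.22 SD.
- ICC 0.5: effective number 33, half-width 0.37 SD.

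The family count alone therefore does not fix the precision.

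**The case against.** The strongest reply is that the plan never claims safety. It states no tolerability hypothesis and gives no rule for reading P≥0.05. A reader might infer that a null result will be presented as proof that reading does not destabilise infants, but that would be a prediction about the report. The document does not say it. This part of the objection stands.

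A second reply concerns size. A reader might infer from 18 families that a large worsening cannot be excluded, or that a non-significant result is to be expected even if events rise substantially. The document supports neither. The analysis is per exposure, 18 is a count of families and not of infants, and exposures and events are not counted. With about 100 events per period and equal observed rates, a doubling would be excluded even at φ=4 (upper limit 1.74). The upper limit near 1.9 belongs only to a setting of about one event per family per period, summed over all exposures. This also stands. If exposures were analysed as independent, P values could be too small, which is a separate problem.

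Third, comparing means and counts by period implies that descriptive summaries will be available, and nothing says that only P values will be shown. That is fair: what is missing is the interval, not every measure of effect.

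None of these replies supplies an interval, so none answers the narrower point.

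**Conclusion.** The concern holds in a limited form. The only inferential criterion is P<0.05, with no planned interval for any contrast, so a non-significant apnea, bradycardia, saturation or oxygen result could not by itself show whether an important worsening had been excluded. That conclusion follows from the text and needs no assumption.

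Its size cannot be settled from the document. At an observed ratio of 1.0, the upper limit on the rate ratio is about 1.9, 1.3 or 1.7 in the three main illustrations. It ranges from about 1.3 to above 5 once event counts from 10 to 100 and variance inflation from 1 to 4 are allowed. These figures rest on assumed totals, equal windows and a large-sample formula, and an observed ratio above 1 would raise every upper limit. They do not show that this study is too small to exclude harm. They show that the planned rule would not reveal whether it is. This is a reporting weakness that should be corrected.

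**What to change.** Replace the final sentence of the Study Protocol section with:

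> For each outcome, report the within-reading difference (rate ratio for events, allowing for window length) with a 95% CI that uses the infant as the unit or adjusts for clustering within infant, and base conclusions on the interval. P≥0.05 alone will not be reported as no effect or well tolerated. Any margin of worsening that the investigators name after data were seen will be labelled post hoc.

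The last clause is needed because the document already reports consent numbers and data exclusions in the past tense, so a margin chosen now may not be prespecified. The report should also give the numbers of infants, exposures and events behind each interval.

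The cost is revised analysis wording, a clustered or infant-level analysis of data already downloaded, and a few extra table columns. The downside is that some statements of no difference will become inconclusive.

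### Six or seven outcomes are each tested against reading at three time points and every P<0.05 counts as significant, with no primary outcome, multiplicity control or exploratory label

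*Combined protocol and SAP*

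**What the plan says.** The outcomes are listed in the final paragraph of the Study Protocol: "Mean RR, HR, apnea and bradycardia episodes, amount of supplemental oxygen needed, mode of respiratory support, if any, and number of periods with oxygen saturation" below 85%. This makes six outcomes if apnea and bradycardia are counted together and seven if they are counted separately.

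Each is compared with the reading period at "3 h before reading, 1 h before reading and 1 h after reading". The reason given is variety: "These time points were chosen to provide a variety of time periods in relation to care times and feedings". The tests are chi-square for categorical and Student's t for continuous variables, and any P below 0.05 "was considered as significant".

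The opening paragraph of the Study Protocol bears on which comparison matters most. It says "Cardiorespiratory events for each reading exposure were compared to the immediate period before and after the reading exposure", and that "the period before each reading exposure served as the control period for that reading exposure".

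Neither paragraph names a primary outcome or a testing order, adjusts for multiplicity or describes the comparisons as exploratory. The text was written after enrolment ("Of 21 sets of parents approached, 18 consented to participate") and after some data had been set aside ("Data from those days were excluded from analysis").

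**The concern.** A single unqualified threshold is applied to every comparison. With 18 to 21 comparisons, an isolated P below 0.05 is close to what chance alone would produce if reading had no effect on anything and each test held its level. The reader cannot tell which result was meant to answer the study question, and the text gives no warning that one significant result among many carries less weight than the 5% label suggests.

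What is at stake is what the study may conclude. Under the stated rule, one favourable contrast, in any outcome and against any of the three windows, can be reported as a significant effect of reading.

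**Working it through.** The plan gives no number of tests, family-wise error rate or power figure, so there is nothing of its own to reproduce. The one stated number is the 0.05 threshold.

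**Inputs from the final paragraph of the Study Protocol**
- Outcomes: m = 6 or 7.
- Comparison time points: 3.
- Threshold: 0.05 for each comparison (sidedness not stated; two-sided assumed below).
- Live and recorded reading are taken as pooled, because separate tests are not described. Testing them separately would double the counts.

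**Number of tests:** 6 × 3 = 18, or 7 × 3 = 21.

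**Expected false positives**, if all nulls are true and each test holds 5%, are 0.05 × k. This needs no assumption about correlation.
- All three time points: 0.05 × 18 = 0.90; 0.05 × 21 = 1.05.
- Contrasts with 1 h before reading only: 0.05 × 6 = 0.30; 0.05 × 7 = 0.35.

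**Chance of at least one false positive if the tests were independent:** 1 − 0.95^18 = 60.3%; 1 − 0.95^21 = 65.9%.

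**The same chance with correlated tests.** All contrasts share one reading period and the same infants, so independence is unlikely. The documents give no correlations, so those below are assumptions. Multivariate-normal simulation, two-sided |z| > 1.96:

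| Correlation between contrasts | Correlation between outcomes | 18 tests | 21 tests |
|---|---|---|---|
| 0.5 | 0 | 55% | 61% |
| 0.5 | 0.3 | 51% | 56% |
| 0.5 | 0.5 | 45% | 49% |
| 0.8 | 0.5 | 37% | 40% |
| 0.9 | 0.7 | 26% | 28% |

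**Does each test hold 5%?** The plan does not say whether the t tests are paired or how repeated exposures of one infant are handled. Two assumed cases show that the level can move either way.
- *Unpaired tests on periods correlated at r.* The per-test level is 2 × (1 − Φ(1.96/√(1 − r))), which is 1.9%, 0.56% and 0.19% at r = 0.3, 0.5 and 0.6. Multiplied by 18 to 21 tests, that gives about 0.34–0.40, 0.10–0.12 and 0.03–0.04 expected false positives.
- *Paired tests with repeated exposures treated as independent.* With 5 exposures per infant and an intraclass correlation of 0.1 in the differences, the design effect is 1 + 4 × 0.1 = 1.4. The per-test level is 2 × (1 − Φ(1.96/√1.4)) = 9.8%, giving about 1.8–2.1 expected false positives.

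**The case against.** The strongest reply has three parts.

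**The time points are not wholly without order.** A reader might infer that the plan treats all three windows as equals. The opening paragraph does not support that: its control is the period immediately before reading, which fits 1 h before better than 3 h before. On that reading the core family is 6 or 7 tests with 0.30–0.35 expected false positives, and the other two windows are supporting. This stands as a lean in the text. It is not an explicit ranking, because the final paragraph tests both pre-reading windows and the post-reading one under the same rule. It also leaves the outcomes unranked: even 6 or 7 independent tests would carry a 26–30% chance of at least one false positive (1 − 0.95^6 = 26.5%; 1 − 0.95^7 = 30.2%).

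**The error figures rest on a condition that may fail.** This also stands. Under the assumptions above, the expected count for 18 to 21 tests runs from about 0.03 to 2.1, depending on pairing and clustering. A reader might infer that the plan has a known false-positive risk of about two in three. The documents do not support that, because it needs independent tests that each hold 5%, and neither is established.

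**The study makes no confirmatory claim.** It has 18 consenting sets of parents, each exposure acts as its own control, and no formal hypothesis or power claim is stated. This lowers the weight of the point but does not remove it. The text does not call the study exploratory, and it attaches the word significant to every comparison below 0.05.

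**Conclusion.** The concern holds in a conditional form. The plan applies an unadjusted 0.05 rule to 18–21 comparisons, names no primary outcome and gives no exploratory label. If all nulls are true and each test holds 5%, about one false positive is expected (0.90–1.05), or about a third of one if only the 1 h-before contrasts count. The chance of at least one among the 18–21 tests is then 60–66% under independence and about 26–61% over the assumed correlations.

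It does not follow that any particular reported result is false, or that the true family-wise risk is known. What follows is narrower: an isolated P below 0.05 from this set cannot be read as evidence at the 5% level, and the plan does not say which result was meant to answer the question. This should be corrected, because the stated rule changes what the study may conclude. The lack of a confirmatory claim keeps it from being more serious.

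**What to change.** 1. Delete the rule that each P below 0.05 is significant.
2. Report every reading-versus-period contrast as a within-exposure estimate with a 95% confidence interval that accounts for repeated exposures per infant.
3. Label all these results exploratory and state how many comparisons were made.
4. If any result is still to be called significant, confine the claim to direct contrasts of reading with the pre-reading control. Use a test that is valid in small samples and accounts for repeated exposures, with Holm across the outcomes (first step 0.05/6 = 0.0083, or 0.05/7 = 0.0071).
5. Name a primary outcome only if it can be shown to have been chosen before the results were seen. The text postdates enrolment and some data exclusions, so a choice made now would not qualify.

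An overall test across the four periods is not a substitute for item 4, because it can reject when reading does nothing. In a simulation with 18 independent units, one exposure each and independent normal errors, only the 3 h-before window was shifted (by 1 SD) and reading equalled both 1 h windows. A Hotelling test on three degrees of freedom rejected about 78% of the time at 0.05 and about 46% at 0.0083. Windows chosen to vary around care times and feedings could plausibly differ in this way.

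The cost is revised wording and a reanalysis of existing data; no new data are needed. The downside is that isolated results below 0.05 can no longer be claimed as significant.
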